#### Summary of MRI-PDFF Method: ANCOVA

	PART 1			
	PLACEBO (N=NN)	LERONLIMAB 700MG (N=NN)	DIFFERENCE 95%CI (Lower-Upper)	P-VALUE [1]
Number. of Subjects	nn	nn		
Baseline	xx.x (xx.x)	xx.x (xx.x)		
Week 14	xx.x (xx.x)	xx.x (xx.x)		
Change at WK14	xx.x (xx.x)	xx.x (xx.x)		
Baseline Adjusted Change at WK14	xx.x (xx.x)	xx.x (xx.x)	xx.xxx (xx.x) (xx.xxx-xx.xxx)	0.xxx

[1] p-value computed using ANCOVA accounting for treatment and baseline as covariates.

\*Programming note 1: Create similar tables for Method=Non-parametric, change headers and footers accordingly.

\*Programming note 2: Repeat these tables for Part 2.

## STATISTICAL ANALYSIS PLAN (SAP) CD1-NASH-01

Protocol No. CD1-NASH-01	Revision No. Rev. 00	Effective Date: 17-Dec-2021
-----------------------------	-------------------------	--------------------------------

### 9.2.2 Analysis of Secondary Endpoints

The secondary efficacy endpoints will be analyzed as follows:

#### *Analysis of Change from Baseline in Fibro-Inflammatory Activity*

Change from baseline in fibro-inflammatory activity as assessed by cT1 (corrected T1) assessed by multiparametric magnetic resonance imaging (MRI) of liver at week 14 will be summarized. The secondary endpoints including change from baseline in cT1, will be assessed in a manner like the assessment of the primary endpoint.

#### *Analysis of Fibro-Inflammatory Activity Categories*

Frequencies will be computed for cT1 grade categories (Mild:  $1 \geq 800-850$ ) Moderate: (851-999, Severe: ( $\geq 1000$ ) and treatment. The treatment groups will be compared using Cochran-Mantel Haenszel chi-square (CMH) test.

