#### 8.1.4 Derived data

BMI : Body Mass Index is the weight in kilograms divided by the square of height in meters

BMI category: Based upon the calculated value of BMI, patients will be categorized into the subcategories

- Underweight : <18.5
- Healthy weight : 18.5 – 24.9
- Overweight : 25.0 – 29.9
- Low risk obesity : 30.0 – 34.9
- Moderate risk obesity : 35.0 – 39.9
- High risk obesity : >=40.0

Heart rate: the measurements will be categorized as

- Slow: <60 beats per minute
- Normal : 60-100 beats per minute
- Fast :>100 beats per minute

Blood pressure: To evaluate blood pressure results of systolic and diastolic measurements are combined to denote hypertension

- Hypertension: Systolic>=140 and Diastolic>=90
- No hypertension : All other combinations

Duration of NASH diagnosis: Time period in years between date of initial NASH diagnosis and randomization date in the study

Grade change from baseline to week 14 in CT1 by degree of fibrosis

- In patients with CT1 800-849 msec mild
- In patients with CT1 850-999 msec moderate
- In patients with CT1  $\geq$  1000 msec severe

End of Treatment (EOT): Subjects who complete the treatment period of 13 weeks have reached their End of Treatment.

Early Termination (ET): Subjects who meet any criteria for discontinuation of study treatment, as specified in Section 5.1 of the protocol, will undergo Early Termination (ET).

Medications:

- Concomitant medications will be coded using WHO dictionary and associated with ATC levels 1 and 2:

Adverse Events:

- Treatment Emergent AE's (TEAE) are defined as events with an onset on or after the first treatment.

	STATISTICAL ANALYSIS PLAN (SAP) CD1-NASH-01		
	Protocol No. CD1-NASH-01	Revision No. Rev. 00	Effective Date: 17-Dec-2021

- System Organ Class (SOC) and preferred terms (PT) will be associated with each adverse event using most recent version of Medical Dictionary for Regulatory Activities (MedDRA).

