## 9 STATISTICAL METHODS

### 9.1 GENERAL STATISTICAL CONSIDERATIONS

All statistical summaries and analyses will be performed using SAS® for Windows, version 9.4 or later.

Collected study data will be presented in subject data listings.

For continuous variables descriptive statistics (n, mean, standard deviation, median, minimum and maximum) will be presented by treatment group.

For categorical variables data summaries by treatment group will include frequency counts and percentages.

Formal treatment group comparisons will be made at the nominal two-sided 0.05 level of significance using the FAS and PP analysis sets. The 95% confidence intervals and p-values for comparing treatment groups will be computed.

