### 9.1.6 Demographic and Baseline Disease Characteristics

Demographics and baseline disease characteristics medical history, prior and concomitant medications/therapies will be summarized by treatment group

The following variables will be summarized descriptively using frequency counts and/or summary statistics n, mean, sd, median, min and max, as appropriate:

VARIABLE	TYPE	PRESENTATION
Age	CONT	In years
Gender	CAT	Male vs Female
Racial categories	CAT	Non-Hispanic Caucasian Hispanic Black/African American Asian Natives Other

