#### Summary of Fibro-Inflammatory Activity Grades Based on cT1 Scores n (%)

	PLACEBO (N=XX)	LERONLIMAB 700 MG (N=XX)	PART 1*	
			P-VALUE [1]	
Mild ( $1 \geq 800-850$ )	n (xx)	n (xx)		
Moderate (851-999)	n (xx)	n (xx)		
Severe ( $\geq 1000$ )	n (xx)	n (xx)	0.xxx	

[1] p-value computed using CMH chi-square test.

\*Programming note: Repeat summary table for Part 2

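### The cT1 grade table and its CMH test name no visit and have no category below 800 ms, the entry minimum, so at week 14 a patient who improves past that point has no cell

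*SAP*

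**What the plan says.** SAP 9.2.2, under Analysis of Fibro-Inflammatory Activity Categories, says "Frequencies will be computed for cT1 grade categories" by treatment, and then "The treatment groups will be compared using Cochran-Mantel Haenszel chi-square (CMH) test". The printed shell has three rows (Mild, Moderate, Severe), a p-value and no visit. Its footnote reads "Programming note: Repeat summary table for Part 2".

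The subsection falls under a heading that opens "The secondary efficacy endpoints will be analyzed as follows", although SAP 3.3 lists the grades as exploratory. SAP 9.1 adds "Formal treatment group comparisons will be made at the nominal two-sided 0.05 level of significance using the FAS and PP analysis sets".

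SAP 8.1.4 defines a derived variable, "Grade change from baseline to week 14 in CT1 by degree of fibrosis", whose first line is "In patients with CT1 800-849 msec mild". SAP 9.1.6 says of baseline data "The following variables will be summarized descriptively using frequency counts and/or summary statistics n, mean, sd, median, min and max, as appropriate", and its list carries cT1 as a continuous variable only.

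Protocol 3.3, inclusion criterion 3, requires cT1 of at least 800 ms at Screening. Protocol 7.14 schedules the liver MRI at Screening and at the End of Treatment (EOT) or Early Termination (ET) visit only.

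**The concern.** The lowest grade begins exactly where eligibility begins. As a description of patients at entry, that is complete. As an outcome scale at week 14, it can record worsening but not improvement below 800 ms.

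The SAP gives no rule for such a patient. A programmer would have to drop the value, fold it into Mild or invent a row. Dropping removes the best outcomes, and more of them from the better arm, so it pulls the comparison toward no difference. Folding keeps the patient but hides improvement past the entry threshold. A between-arm p-value, produced for Part 1 and repeated for Part 2, would rest on a choice that could be questioned as data-driven if made after unblinding.

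**Working it through.** **1. Grade limits side by side (ms)**

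| Place | Mild | Moderate | Severe | Below 800 | Visit |
|---|---|---|---|---|---|
| SAP 3.3 | 800–850 | 851–999 | ≥1000 | none | none |
| SAP 8.1.4 | 800–849 | 850–999 | ≥1000 | none | baseline to week 14 |
| SAP 9.2.2, text and shell | 800–850 | 851–999 | ≥1000 | none | none |

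SAP 3.3 also lists an overlapping Mild-Moderate group, 800–999. The Mild limit in 9.2.2 is garbled in the available text, but 3.3 and 8.1.4 both confirm the 800 ms floor.

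Trial values: 760 and 799 have no cell under any list. 850 is Mild in two places and Moderate in the third. 850.5 has no cell in 3.3 or 9.2.2, and 999.5 has none in the three separate grades anywhere.

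**2. Which visit?** cT1 exists only at Screening and EOT/ET. Four things point to week 14: the placement under secondary efficacy, the treatment-group test, the 8.1.4 grade change to week 14, and the continuous-only baseline listing. The overlapping group in 3.3 and the patient-group wording of 8.1.4 also fit baseline subgroups.

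**3. How often would a week-14 value fall below 800?** The plan has no figure to reproduce, so the inputs are assumed: mean change 0 to −60 ms, SD of change 40 to 70 ms. For baseline b, P(below 800) = Φ[(800 − b − mean change)/SD].

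- b = 850, change 0, SD 40: Φ(−50/40) = Φ(−1.25) = 11%
- b = 850, change −60, SD 40: Φ(10/40) = Φ(0.25) = 60%
- Ranges over the assumptions: b = 810, 40–89%; b = 850, 11–60%; b = 900, 1–28%; b = 950, 0–10%

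**4. One assumed table, 30 per arm** (below 800 / Mild / Moderate / Severe): placebo 3/7/14/6, leronlimab 12/5/9/4. The mean-score CMH is Q = (N − 1)r² on 1 df, with scores 0 to 3.

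- Own row: means 53/30 = 1.767 and 35/30 = 1.167. Between-group SS = 15 × 0.6² = 5.4; total SS = 194 − 88²/60 = 64.93. Q = 59 × 5.4/64.93 = 4.91, p = 0.027.
- Dropped (27 v 18): means 53/27 = 1.963 and 35/18 = 1.944. Q = 0.007, p = 0.93.
- Folded into Mild: means 56/30 = 1.867 and 47/30 = 1.567. Between-group SS = 15 × 0.3² = 1.35; total SS = 209 − 103²/60 = 32.18. Q = 59 × 1.35/32.18 = 2.48, p = 0.12.

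**5. Simulation** (4,000 trials per setting, 30 per arm). Eight assumed baseline distributions were truncated at 800 (resulting means 856–964, SDs 40–92 ms) and crossed with SD of change 40, 50 or 70, giving 24 settings per effect. Grades were below 800, 800 to <851, 851 to <1000 and ≥1000. Ranges are the minimum and maximum over settings.

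| Assumed effect | Dropped | Folded into Mild | Own row |
|---|---|---|---|
| 40 ms | 12–25% | 21–54% | 23–71% |
| 60 ms | 18–41% | 42–85% | 46–96% |
| 60 ms, the 15 settings with baseline mean 887–935 | 18–41% | 50–82% | 56–89% |
| 80 ms | 25–58% | 64–96% | 70–100% |

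With no effect, 3–25% of each arm falls below 800, and type I error is 4.2–5.9% for all three options. At 60 ms, 15–55% of active and 3–25% of placebo fall below 800. Within a setting at 60 ms, the row gains 22–65 points over dropping but only 2–12 over folding. With the general-association CMH at 60 ms, dropping gives 12–30% and the row 30–90%. ANCOVA on continuous cT1 change has 89–100% power at 60 ms.

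**The case against.** The documents do not settle the visit. A floor equal to the entry minimum, an overlapping group in 3.3 and the wording of 8.1.4 all suit baseline strata, and on that reading no eligible patient is lost below 800 ms. This stands as a reason to keep the missing-cell point conditional. It does not rescue the table, because a test of baseline grades between arms is not an efficacy analysis.

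The SAP also never says such values are dropped. SAP 8.1.2 uses data as observed, which weighs against dropping, and percentages on the full arm size would visibly fail to reach 100. SAP 8.1.1 allows analyses to be updated when the data structure does not fit, and 9.1.1 promises a separate shell document, which is not among the documents reviewed. All of this is fair, and against folding the loss is modest. Still, neither 8.1.1 nor 8.1.2 assigns the value a category, and the shell printed in the SAP has no row for it.

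Finally, every magnitude rests on assumed inputs, P-values by grade are exploratory, the sample size was not set by power (Protocol 8.3), and the protocol's outcome list has no categorical cT1 endpoint. These points limit the consequence. They do not remove the defect.

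**Conclusion.** The concern holds. Three facts do not depend on interpretation: SAP 9.2.2 names no visit for the grade table or its test, no grade list reaches below the 800 ms entry minimum, and 850 ms is graded two ways. The missing cell is a fault if the table is week 14, which is likelier but not stated.

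Only the direction of the effect is firm: dropping values below 800 biases toward no difference. The power figures depend on assumed baselines, change SDs and effects, and most of them on a mean-score CMH that the SAP does not name. The harm is confined to an exploratory grade comparison and its Part 2 repeat. The primary endpoint and the continuous cT1 analysis are untouched. It should be fixed, but it does not threaten the main conclusions.

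**What to change.** Before database lock and unblinding:

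- State the visit and purpose of the grade table and its test, including whether an ET scan counts as week 14.
- If it is week 14, add a row below 800 ms to the table and to any week-14 grade or grade-change definition in SAP 8.1.4. Count every patient in the full analysis set (FAS) with a week-14 cT1 in the denominator.
- Use one gap-free set of limits in 3.3, 8.1.4 and 9.2.2, for example <800, 800 to <850, 850 to <1000 and ≥1000 ms.
- Name the row-mean-score CMH, since the grades are ordered.
- If the groups in 3.3 or 8.1.4, including Mild-Moderate, are baseline subgroups, label them so and keep them apart from the week-14 grades. They need no row below 800, only a rule for an enrolled eligibility violator, who leaves the per-protocol set (SAP 2.9.1) but may stay in the FAS (SAP 7.1).

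The cost is SAP and table-shell wording. No new data are needed.

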#### Summary of Fibro-Inflammatory Activity Grades Based on cT1 Scores n (%)

	PLACEBO (N=XX)	LERONLIMAB 700 MG (N=XX)	PART 1*	
			P-VALUE [1]	
Mild ( $1 \geq 800-850$ )	n (xx)	n (xx)		
Moderate (851-999)	n (xx)	n (xx)		
Severe ( $\geq 1000$ )	n (xx)	n (xx)	0.xxx	

[1] p-value computed using CMH chi-square test.

\*Programming note: Repeat summary table for Part 2

#### *Analysis of Other Continuous Secondary Endpoints*

Change from baseline to Week 14 in the continuous secondary endpoints will be analyzed using methods like the one used for the primary endpoint.

- liver fibrosis using FibroTest at week 14
- hepatic inflammatory activity using FibroTest at week 14
- serum pro-inflammatory biomarkers assessments
- Gamma-glutamyltransferase (GGT) at week 14
- Cytokeratin 18 (CK-18) level at week 14
- Leronlimab (PRO 140) PK assessments

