8.3 SAMPLE SIZE DETERMINATION AND RATIONALE

The sample size of 90 total subjects [60 subjects (30 subjects per arm) for the Randomized Phase and up to 30 subjects for the non-randomized, open-label phase] is selected on the basis of clinical judgment and not based on statistical power calculation. The number of subjects is deemed adequate to provide clinically meaningful descriptive results consistent with study objectives.

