8.4 RANDOMIZATION

Subjects who are eligible to participate in the trial will be randomized to one of the treatment groups via IWRS (Interactive Web Based Randomization System) at the T1 Visit prior to IP administration. The randomization will be central and will use 1:1 ratio of Treatment groups A and B:

- PRO 140 700mg SC weekly injection (Group A)
- Placebo 0 mg SC weekly injection (Group B)

Note: Randomization is not applicable for the open-label, single-arm portion (Part 2) of the study.

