8.8 ANALYSIS METHODS

A SAP will be developed and approved before the database is locked. The SAP will present the detailed statistical methodology to be used in analyzing the data from this trial. All inferential statistical analysis will be based on a two-sided test with a Type I error rate of 0.05.

All the efficacy analyses presented here will be conducted using both the ITT and PP populations. All safety analyses will be conducted using the Safety population. Continuous data summaries will

include number of observations, mean, standard deviation, median, and minimum and maximum values. Categorical data summaries will include frequency counts and percentages.

Subject Disposition

The disposition of all subjects who sign an ICF will be provided. The numbers of subjects screened, randomized, received treatment, completed, and discontinued during the study, as well as the reasons for all post-enrollment discontinuations will be listed and/or summarized by treatment group.

Demographic and Baseline Disease Characteristics

Demographics and baseline disease characteristics including medical history, prior and concomitant medications/therapies will be listed and/or summarized by treatment group using appropriate descriptive statistics.

Study Analyses

Efficacy Analysis

Analysis of the efficacy endpoints will be conducted according to below methods:

- If the Normality assumption is met, Analysis of Covariance (ANCOVA) or Mixed Model using the covariates in the model.
- If the Normality assumption is not met, a non-parametric method or a rank – ANCOVA analysis will be used.

Safety Analyses

Safety will be assessed by close monitoring and timely assessment of adverse events (AEs), laboratory parameters (blood tests, urinalysis), vital signs (blood pressure, heart rate), subject's medical condition (physical examination including weight). Tolerability of repeated subcutaneous administration of Leronlimab (PRO 140) as assessed by study participants (using 11-point Numeric Pain Rating Scale) and by investigator-evaluation of injection site reactions.

Adverse Events

Adverse events will be coded using the most recent version of Medical Dictionary for Regulatory Activities (MedDRA). Treatment Emergent AE's (TEAE) are defined as events with an onset on or after the first treatment. TEAEs will be summarized by treatment group, System Organ Class, and preferred term. The following TEAE summaries will be provided:

- by PT in descending order of frequency

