### 9.2.1 Analysis of Primary Efficacy Endpoint

The null hypothesis of no between treatment group difference in mean change from baseline in hepatic fat fraction assessed by magnetic resonance imaging-derived proton density fat fraction (MRI-PDFF) at week 14 against alternate hypothesis of a non-zero treatment-difference will be tested at 0.05 level of significance.

A preliminary assessment of normality will be performed using Shapiro-Wilks test at the 5% significance level.

If departure from normality is not concluded a normality-based parametric test of the null hypothesis will be performed using ANCOVA with baseline as a continuous covariate and treatment group as a categorical covariate. The point estimate of the mean (SD) along with corresponding 95% confidence interval will be presented. The baseline adjusted estimates of the treatment means and treatment difference along with 95% confidence interval and the two-sided p-values will be presented.

Otherwise, the null hypothesis will be tested using the two-sample Wilcoxon Rank Sum test and the Hodges-Lehmann estimate of location shift along with the corresponding 95% confidence intervals will be reported.

Even if the parametric analysis is deemed appropriate, the non-parametric analyses will be performed to assess the robustness of the conclusions based on ANCOVA.

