### *Analysis of Continous Exploratory Endpoints*

Change from baseline to Week 14 in the continuous exploratory endpoints will be analyzed using methods like the one used for the primary endpoint.

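### Skewed laboratory markers are tested as untransformed change with a fallback that drops baseline; a pre-specified log-scale ANCOVA would gain about 5 to 30 points of power under stated assumptions

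*SAP*

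**What the plan says.** SAP 9.2.2 lists the two FibroTest scores, the serum pro-inflammatory biomarkers, GGT, CK-18 and PK, and states: "Change from baseline to Week 14 in the continuous secondary endpoints will be analyzed using methods like the one used for the primary endpoint". SAP 9.2.3 covers ALT, AST, total bilirubin, triglycerides and LDL: "Change from baseline to Week 14 in the continuous exploratory endpoints will be analyzed using methods like the one used for the primary endpoint".

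The primary method (SAP 9.2.1) begins with a Shapiro-Wilk test at 5%. If normality is not rejected, the untransformed change is analysed by ANCOVA with baseline and treatment. "Otherwise, the null hypothesis will be tested using the two-sample Wilcoxon Rank Sum test", with a Hodges-Lehmann shift and no baseline term. The SAP does not say whether normality is tested on the change or on the model residuals. No transformation is planned for any endpoint.

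Three other places bear on this. SAP 9.1.2 and the Covariates paragraph of Protocol 8.7 make baseline a covariate for efficacy analyses. Protocol 8.8 allows either a non-parametric method or rank-ANCOVA when normality fails. SAP 8.1.2 rules out imputation of missing data points.

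The comparisons are inferential: "Formal treatment group comparisons will be made at the nominal two-sided 0.05 level of significance using the FAS and PP analysis sets".

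**The concern.** Serum enzymes, cytokines and triglycerides are plausibly right-skewed, and a treatment effect on them may act as a proportion of the starting value. If so, a few subjects with high baselines dominate the raw change, and a shift in IU/L or pg/mL means different things in subjects with different baselines.

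On such data the normality test often rejects. The analysis then moves to a test that leaves out baseline, although the SAP's own covariate rule calls for it. Two separate losses result, one from the scale and one from the missing covariate.

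At stake is the chance of detecting a real effect on these secondary and exploratory markers, using data already collected, in a trial whose size was not set by power.

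**Working it through.** **Inputs from the documents.** Two-sided test at 5% (Protocol 8.8: "All inferential statistical analysis will be based on a two-sided test with a Type I error rate of 0.05"). Part 1 size: "60 subjects (30 subjects per arm) for the Randomized Phase", allocated 1:1 (Protocol 8.4). The sample size rests on "clinical judgment and not based on statistical power calculation", so there is no planned power to reproduce. For orientation, 30 per arm gives 80% power for a difference of about 0.72 SD.

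**Assumed inputs, not in the documents.** Baseline and week-14 values are bivariate log-normal with log-SD s of 0.3, 0.5, 0.7 or 1.0 and log-scale correlation ρ of 0.5, 0.7 or 0.85. The effect is proportional.

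**Methods compared** (1,500 simulated trials per cell)
- SAP rule: Shapiro-Wilk at 5% on the change, then ANCOVA of raw change on baseline and treatment, otherwise Wilcoxon on raw change.
- Log-ANCOVA: log(week 14) − log(baseline) on log(baseline) and treatment.

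**Formula check.** For log-ANCOVA the standardised effect is |ln(ratio)| / (s·√(1 − ρ²)). With s = 0.7, ρ = 0.7 and ratio 0.697: 0.361 / (0.7 × 0.714) = 0.72, so about 80% power. The simulation gives 78%. In the same cell raw-change ANCOVA gives 64%, Wilcoxon 55% and the SAP rule 56%, a gain of 22 points.

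**Gain of log-ANCOVA over the SAP rule**, effect set so that log-ANCOVA has about 80% power:

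| log-SD | ρ = 0.5 | ρ = 0.7 | ρ = 0.85 | Trials sent to Wilcoxon |
|---|---|---|---|---|
| 0.3 | +6 | +4 | +5 | 16–24% |
| 0.5 | +16 | +15 | +12 | 52–59% |
| 0.7 | +26 | +22 | +17 | 82–88% |
| 1.0 | +33 | +26 | +23 | 97–99% |

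Simulated type I error is about 4–6% for both methods, so the gain is not bought with false positives.

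**Sensitivity**
- Fixed 25% reduction: 0 to +2 points at log-SD 0.3, where power is already near 100%; +4 to +15 at 0.5; +15 to +17 at 0.7; +9 to +16 at 1.0.
- 25 per arm: +3 to +31 points.
- Normality test applied to residuals: mostly similar. The largest shift is at log-SD 0.3, ρ = 0.5, where the gain rises from about 6 to about 13 points.
- Additive effect on near-normal data (CV 0.2–0.3): log-ANCOVA loses about 0.5 to 6 points.

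**How much comes from dropping baseline.** On a normal scale, the variance of the ANCOVA estimate relative to that of unadjusted change is (1 + ρ)/2: 0.75, 0.85 and 0.925 at the three correlations. Using the Wilcoxon test's efficiency of 0.955 on normal data, an 80% powered ANCOVA becomes Φ(2.80·√(0.955·(1 + ρ)/2) − 1.96) = 66%, 71% and 75%. Dropping baseline therefore costs about 14, 9 and 5 points with the scale already right.

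The simulations show the same split. At log-SD 0.7, correlation 0.75, ratio 0.70 and 30 per arm, repeat runs give 61–65% for the SAP rule, 73–75% for rank-ANCOVA of raw change and 82–84% for log-ANCOVA. Taking the lowest set, 12 of 21 points come back with rank-ANCOVA alone; taking the highest, 10 of 19. Roughly half is thus a covariate problem. That share should not be carried to log-SD 0.3, where the normality test mostly leaves the baseline-adjusted ANCOVA in place.

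**The case against.** The strongest reply is that the model favours the remedy. Exactly log-normal data with an exactly proportional effect is the setting in which log-ANCOVA does best, and no figure in the documents shows that these markers behave so. That stands, and it is why the gain is given as a conditional range with the additive case beside it.

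The plan also has some defence. Baseline-adjusted ANCOVA is the first-line test, so the unadjusted test applies only after rejection. SAP 8.1.1 lets analyses be updated if assumptions fail. But that leaves any transformation to be chosen once the data are in hand. The sample size is described as adequate for descriptive results, and these are secondary and exploratory endpoints. That limits the weight of the point, but SAP 9.1 still attaches p-values and confidence intervals to them.

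Several stronger readings are tempting and are not supported:
- **A fixed gain of 10 to 20 points.** This describes the middle of the assumed grid. Mildly skewed markers gain less and strongly skewed ones more.
- **A documented 20-fold spread.** Eligibility admits ALT below 5 × 63 = 315 or 5 × 54 = 270 IU/L, against lower normal limits of 17 and 14. The ratios of about 19 describe an admissible span, not a distribution. The ceiling covers only AST, ALT and ALP, and says nothing of GGT, CK-18, triglycerides or cytokines.
- **The protocol itself scales these markers proportionally.** The multiples of baseline in Protocol 5.1 belong to a liver-safety rule for AST, ALT and bilirubin. They do not settle the scale of an efficacy analysis.
- **Scale is the whole problem.** Rank-ANCOVA on raw change recovers about half the gap in the cell above.
- **Most endpoints are affected.** By the lists in SAP 3.2 and 3.3 it is 3 of 7 Part 1 secondary items (cytokines, GGT, CK-18) and 3 of 8 exploratory items (ALT, AST, triglycerides).
- **The Wilcoxon test breaches Protocol 8.8.** It does not, since that section allows a non-parametric method. The conflict is with the covariate rule in SAP 9.1.2 and Protocol 8.7.

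**Conclusion.** The point holds as a conditional efficiency loss with two sources: the untransformed scale, and a fallback that omits baseline against the SAP's own covariate rule. Under log-normal data with proportional effects, log-SD 0.3 to 1.0, correlation 0.5 to 0.85 and 30 per arm, log-scale ANCOVA gains about 5 to 30 points (simulated +4 to +33) when it has about 80% power. Little is gained where power is already near 100%, and about 0.5 to 6 points are lost if effects are additive and data near normal. All of these inputs are assumptions. The covariate conflict is the part that rests on the documents alone.

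This is a worthwhile improvement to secondary and exploratory analyses. A reader should not infer that the primary PDFF conclusion is at risk, because the proposal does not touch it.

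**What to change.** Before database lock and unblinding, amend SAP 9.2.2 and 9.2.3 as follows.

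- For GGT, CK-18, ALT, AST, triglycerides and each cytokine, pre-specify ANCOVA of log(week 14) − log(baseline) on log(baseline) and treatment. Report the geometric mean ratio versus placebo with its 95% CI.
- Replace the unadjusted Wilcoxon test with rank-ANCOVA including baseline, as fallback or robustness check. This satisfies SAP 9.1.2 and is already allowed by Protocol 8.8.
- Keep FibroTest/ActiTest scores, cT1 and total bilirubin on their own scale. The case for logging bilirubin is weak, since entry is capped at 1.3 mg/dL except in Gilbert's disease.
- State that values below the quantification limit are set to half that limit as an assay convention. Reconcile this with the no-imputation rule in SAP 8.1.2 and Protocol 8.7, for example by saying that such a value is a censored measurement and not a missing one.
- Record the change in SAP section 10.

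The cost is SAP wording and table headers; no patients or visits are added. There are two downsides. The effect measure becomes a ratio, so the endpoint descriptions need a line saying that change is expressed on the log scale. Analytes with many values below quantification stay weakly informative, and the simulations above included no such values.
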